8.1.3. Standardization of study condition

Subjects stay at the study site one night before and during the sampling period for at least 24 hours after drug administration. Subjects are admitted to the study wards at PT. Pharma Metric Labs in the evening before the study day. Subjects are instructed to fast from 8 hours before until 4 hours after drug administration. Food intake during the study period will be standardized for all subjects. The menu served and meal taken by subjects at every study period should also be recorded. Water can be consumed as desired except during the period of 1 hour before and 2 hours after drug administration.

8.1.4. Drug administration

At approximately 1 hour before drug administration, the subjects undergo physical examination for baseline vital sign data (body temperature, blood pressure, heart rate/pulse, and respiration rate). Female subjects of child-bearing age must undergo urinary pregnancy test. The data will be recorded in the CRFs.

As scheduled, starting at 07:00 in the morning of the sampling day, subjects are given a single dose of cyproterone acetate and ethinyl estradiol of either formulation (test or reference) with 240 ml of water. Subjects administer the drug products in sitting posture. Subjects are asked to maintain upright position (standing or sitting) for 1 hour after drug administration.

8.1.5. Pharmacokinetic sampling

Blood samples for cyproterone acetate and ethinylestradiol assay (approximately 6 ml) are drawn into tubes containing anticoagulant (EDTA) before drug administration (0 h) and 15, 30, 45 min, 1, 1.5, 2, 2.5, 3, 4, 5, 6, 9, 15, 24, 36, 48 and 72 hours after drug administration. Whole blood samples are collected from fresh clean venipuncture using disposable sterile syringe and needle.

The predose sample is collected within an hour before the first drug dosing SN01. A total volume of 216 ml of blood will be collected from each subject (2 periods x 18 sampling points x 6 mL per sampling points) of 108 mL per period. This volume of blood was used for pharmacokinetic analysis.

Collected blood samples are centrifuged at 3000 rpm for 10 mins using centrifuge with 32-cm rotor diameter, plasma is separated and stored frozen at a maximum temperature of -20°C until assayed.

8.1.6. Labeling of the samples

The blood collection tubes are labeled with the study number, study period, subject number and sample code, e.g. P1, T1, SN01, 440 is period 1, sample 1, subject 01, study number 440.

8.1.7. Subject monitoring

During the study period all subjects are under direct supervision by Study Physician at the study site. A brief clinical history interview and physical examination must be conducted a day before the study, and repeated again before patient discharge.

Vital signs (blood pressure, pulse, respiration rate and body temperature) are also monitored and recorded in the CRF. The baseline vital signs should be measured prior to drug administration, and subsequently at 1, 3, 5, 9, 15, 24, 36, 48 and 72 hours after drug administration. These vital signs can be measured before or after blood collection. If the vital signs are outside the normal limit, the physician will take action needed to normalize the condition or withdraw the subjects from the study. Any adverse events which may occur during the study are monitored and should also be recorded in the CRF.

8.1.8. Removal of Subject from assessment

Subjects may withdraw, at their own request, from the study at any stage. If the subject discontinues from the study at any time after being assigned to a subject number, the CRF must be completed accordingly. Subjects may be discontinued from the study for any of the following reasons:

- a. Subjects wish to withdraw from the study, irrespective of the reason,

- b. Adverse event of the study drug,
- c. Illness requiring medication that interfere with the pharmacokinetics of the study drug,
- d. Protocol violation by the subjects that interfere with the pharmacokinetics of the study drug,
- e. Pregnancy test is positive
- f. Subject vomited on or before $2x$ median of t_{max} under BE study of immediate release drug, or vomited after dosing and within blood sampling period under BE study of modified release drug,
- g. Subject experienced diarrhea within blood sampling period.

The Investigator is free to discontinue any subject participation in the study if in her opinion, continued participation is not in the subject interest or may jeopardize the subject health. The subject must be withdrawn from further participation in the study if they develop a serious adverse event that may be related to drug administration.

8.2. Study Treatments

8.2.1. Drug accountability

The test drug with the certificate of analysis and the reference drug are supplied by the sponsor. The certificate of analysis contains product description, results of test as per protocol specifications/pharmacopoeia. In vitro dissolution data is desirable if it is available. The drug is stored in a locked drug storage area. The Responsible Pharmacist is accountable for the study drug. The dispensing and inventory records are kept in the study site file. This record is available for inspection by the sponsor or the regulatory personnel. The sponsor will have to supply a sufficient number of study drugs.

At the end of the study, all unused medications (test and reference drugs) will be returned to the sponsor or destroyed if authorized by the sponsor.

8.2.2. Coding / labeling of the drug used in the study

The label of the study drug is as following:

No. of study protocol	: 440/STD/PML/2018
Reference Drug	: Diane [®] -35
Manufactured by	: Bayer Weimar GmbH, Germany for Pharma AG, Germany, imported by PT. Bayer Indonesia, Depok, Indonesia
Batch Number	: 71533A
Manufacturing date	: March 2017
Expiration date	: March 2020
Mode of administration	: per oral (po)
Storage Condition	: Store below 25°C
CAUTION	
FOR CLINICAL STUDY ONLY	

No. of study protocol	: 440/STD/PML/2018
Test Drug	: Elzsa [®] film-coated tablet
Manufactured by	: PT. Sydna Farma
Batch Number	: TR20745
Manufacturing date	: August 2018
Expiration date	: August 2020
Mode of administration	: per oral (po)
Storage Condition	: Store below 25°C

CAUTION
FOR CLINICAL STUDY ONLY

8.2.3. Blinding

The drug allocation information is limited to the Data Management Officer only. The rest of the study team members are blinded to the treatment sequence.

8.2.4. Randomization

The randomization is performed using block randomization, and the Test-Reference and Reference-Test sequences are balanced. The randomization code is provided by the Data Management Officer, sealed and stored in a locked place, and is limited to the Data Management Officer only.

The code breaking (decoding) will be carried out after all blood samples are completely analyzed and just before the statistical analysis. The sponsor's representative will open the randomization code.

8.2.5. Drug administration

On the sampling day as per schedule, subjects are given a single dose of cyproterone acetate and ethinyl estradiol of either formulation (test or reference) with 240 ml of water.

8.2.6. Washout period

Washout period is determined based on the half-life of the study drug (analyte). At least 5 times elimination half-life is necessary. The wash out period for this study is three weeks. After a washout period, the study is repeated in the same manner with the alternate drug.

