are collected from fresh clean venipuncture using disposable sterile syringe and needle. Collected blood samples are centrifuged at 3000 rpm for 10 minutes using 32-cm rotor diameter centrifuge. Separated plasma is then stored frozen at a maximum temperature of -20°C until assayed.

Standardized meals are served 4 hours after drug administration. A record of the menu served and meal taken by subjects at every study period will be maintained.

After a washout period of three weeks, the study will be repeated in the same manner with the alternate drug.

The subjects' safety is monitored during the entire study. They are under direct supervision by Study Physician at the study site. Vital signs (blood pressure, pulse, respiration rate and body temperature) are monitored and recorded in the Case Report Form.

Analytical Procedures

Plasma concentration of cyproterone acetate and ethinylestradiol will be measured by a validated LC-MS/MS method.

Plasma containing cyproterone acetate and ethinyl estradiol is spiked with internal standard solution and blended well. The drug is then extracted using an organic solvent. The organic layer is transferred to a clean glass tube and evaporated to dryness under nitrogen stream in a water bath. The residue is then reconstituted with organic solvent and an aliquot is injected into the LC-MS/MS system. The LLOQ is 0.4 ng/ml and 4.99 pg/ml for cyproterone acetate and ethinylestradiol, respectively.

Statistical Procedures

The area under the cyproterone acetate and ethinylestradiol concentration versus time curve from 0 to 72 hours (AUC_t) is then calculated using trapezoidal rule. Bioequivalence of the two formulations will be assessed by comparing the AUC_t and C_{max} of cyproterone acetate and ethinyl estradiol values after ln transformation of the concentration data. The geometric mean ratios (test/reference) of the ln-transformed data and their 90% confidence intervals will be further analyzed with a parametric method (analysis of variance/ANOVA) using Equiv Test[®] version 2.0 (Statistical Solution Ltd., Saugus, MA, USA), or manual calculation which has been validated to Equiv Test[®].

Bioavailability Parameters and Bioequivalence Criteria

The two products are considered bioequivalent when the 90% confidence intervals of the cyproterone acetate and ethinyl estradiol geometric mean ratio between test and reference product fall within the range of 80.00-125.00% for AUC_t and C_{max} .

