5.2 Pharmacokinetic properties

Absorption

Following oral administration cyproterone acetate (CPA) is completely absorbed over a wide dose range. Peak serum concentrations of 15 ng/mL are reached at about 1.6 hours after single ingestion. The absolute bioavailability of cyproterone acetate is unknown. Relative bioavailability was calculated, in a study of eight young women, from a dose-corrected comparison of area under the curves (AUC) of serum levels after 100 mg oral and 300 mg intramuscular depot administration and was found to be 80 + 30% when averaged over all volunteers (range 23% - 119%).

Orally administered ethinylestradiol is rapidly and almost completely absorbed. Peak serum concentrations of about 71 pg/mL are reached within 1-2 hours. Absolute bioavailability, as a result of presystemic conjugation and first pass metabolism, is approximately 60%.

Distribution

Cyproterone acetate is almost exclusively bound to serum albumin. Only 3.5 - 4.0% of the total serum drug concentrations are present as free steroid. The ethinylestradiol-induced increase in sex hormone binding globulin (SHBG) does not influence the serum protein binding of cyproterone acetate. The apparent volume of distribution of cyproterone acetate is about 986 ± 437 L.

Ethinylestradiol is highly but non-specifically bound to serum albumin (approximately 98.5%) and induces an increase in the serum concentrations of SHBG. An apparent volume of distribution of approximately 5 L/kg was determined.

Metabolism

Cyproterone acetate is subject to extensive metabolism. The main metabolite in plasma was identified as 15-hydroxy-CPA which is formed possibly via the cytochrome P450 enzyme CYP3A4. The clearance rate from serum is about 3.6 mL/min/kg.

Ethinylestradiol is subject to presystemic conjugation in both small bowel mucosa and the liver. Ethinylestradiol is primarily metabolized by aromatic hydroxylation but a wide variety of hydroxylated and methylated metabolites are formed, and these are present as free metabolites and as conjugates with glucuronides and sulfate. The metabolic clearance rate is about 5 mL/min/kg.

Elimination

Cyproterone acetate serum levels decrease in two phases which are characterized by half-lives of about 0.8 h and about 2.3 to 3.3 days. Cyproterone acetate is partly excreted in unchanged form. Its metabolites are excreted at a urinary to biliary ratio of about 1:2. The half-life of metabolite excretion is about 1.9 days.

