Ethinylestradiol serum levels decrease in two phases, the terminal disposition phase is characterised by half-life of approximately 24 hours. Unchanged drug is not excreted, ethinylestradiol metabolites are excreted at a urinary to biliary ratio of 4:6. The half-life of metabolite excretion is about 1 day.

A bioequivalence study to compare the test product, 2 mg cyproterone acetate/0.035 mg ethinylestradiol fixed-dose tablets and the reference product Diane 35[®] (2 mg cyproterone acetate/0.035 mg ethinylestradiol fixed-dose tablets, Schering France), was performed. The study design was two-way, open, randomised, cross-over study in 35 female postmenopausal healthy volunteers (aged 35-65 years) after single oral dose. The study was clinically well tolerated. The pharmacokinetic parameters of ethinylestradiol are illustrated in Table I and the parameters of cyproterone acetate in Table II.

Table I. Pharmacokinetic parameters of ethinylestradiol

Pharmacokinetic parameters of ethinylestradiol (n=30)			
	Test product	Diane 35 [®]	90% CI
AUC _{0-t} (pg.h/ml)	2044.34 ± 761.49	2026.55 ± 612.80	92.21 – 104.66
AUC _{0-∞} (pg.h/ml)	2274.67 ± 849.00	2229.15 ± 682.69	93.40 – 106.27
C _{max} (pg/ml)	169.23 ± 52.09	177.49 ± 58.72	91.94 – 100.29
t _½ (h)	16.07 ± 4.76	16.82 ± 5.39	
t _{max} (h)	2.0 ± 0.75	2.00 ± 0.50	

Table II. Pharmacokinetic parameters of cyproterone acetate

Pharmacokinetic parameters of cyproterone acetate (n=30)			
	Test product	Diane 35 [®]	90% CI
AUC _{0-t} (pg.h/ml)	318206.1 ± 78626.9	327887.3 ± 85063.0	94.08 – 100.15
AUC _{0-∞} (pg.h/ml)	403149.9 ± 116224.5	428492.9 ± 132888.0	90.70 – 97.75
C _{max} (pg/ml)	27436.24 ± 5872.79	29942.10 ± 7268.07	86.23 – 97.63
t _½ (h)	103.56 ± 24.84	116.81 ± 38.68	
t _{max} (h)	2.00 ± 0.00	1.50 ± 0.50	

A bioequivalence pilot study to compare the test product, 2 mg cyproterone acetate/0.035 mg ethinylestradiol fixed-dose tablets manufactured by PT. Sydna Farma, and the reference product, Diane 35[®] fixed-dose tablets manufactured by Bayer Weimar GmbH, Germany for Bayer Pharma AG, Germany), was performed in 6 healthy female subjects at PT. Pharma Metric Labs, Jakarta. The pharmacokinetic parameters of ethinylestradiol are illustrated in Table III and the parameters of cyproterone acetate in Table IV.

Table III. Pharmacokinetic parameters of ethinylestradiol of the bioequivalence pilot study

Pharmacokinetic Parameter		Test Drug (Lydia [®]) (n = 6) mean (SD)	Reference Drug Diane [®] -35 (n = 6) mean (SD)

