8.5. Statistical evaluation

Bioequivalence of the two drug formulations is assessed by calculating individual AUC_t and C_{max} values. The mean ratio (test/reference) of the ln-transformed data and their 90% confidence intervals is analyzed with a parametric method (analysis of variance/ANOVA) using Equiv Test[®] version 2.0 (Statistical Solution Ltd., Saugus. MA, USA) or manual calculation which has been validated to Equiv Test[®]

90% confidence intervals (90% CIs) are calculated using the following equation :

$$(90\% \text{ CI})_{diff} = \text{difference} \pm t_{0.1 (n-2)} \times SE_{diff}$$

$$\text{difference} = \text{mean of ln T} - \text{mean of ln R}$$

PharmaMetric Labs

n = number of subject

$\alpha = 0.05$

$SE\ diff = (\frac{1}{2}MS_{residual} \times (1/nTR + 1/nRT))^{\frac{1}{2}}$

(90% CI) ratio = anti ln (90% CI)_{diff} X 100%

The two products are considered bioequivalent when the 90% confidence interval of the cyproterone acetate and ethinyl estradiol geometric mean ratio between test and reference product falls within the range of 80.00 - 125.00% for AUC_t and C_{max}.

If a pre-dose concentration of cyproterone acetate and ethinyl estradiol is detected, the subject's data can be included in the pharmacokinetic and statistical analysis without adjustment, if the pre-dose concentration is equal to or less than 5% of the C_{max} value of the corresponding period. If the pre-dose concentration is greater than 5% of the C_{max} value, the subject's data will be dropped from all pharmacokinetic and statistical evaluations of cyproterone acetate and ethinyl estradiol.

Subjects who lack of any measurable concentrations, or have only very low plasma concentrations of cyproterone acetate and ethinyl estradiol for the reference medicinal product, will be excluded from statistical analysis. According to EMA Guidance (CPMP/EWP/QWP/1401/98 Rev.1/Corr**), a subject is considered to have very low plasma concentrations if its AUC is less than 5% of reference medicinal product geometric mean, calculated without inclusion data from the outlying subject. Data (concentrations and pharmacokinetic parameters) from these excluded subjects will be presented but excluded from descriptive statistics. If the study is continued to the second stage, the 94.12% confidence intervals (94.12% CIs) are calculated using $\alpha = 0.0294$.

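### Does the three-week washout break the plan's own five-half-life rule for cyproterone acetate?

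*Combined protocol and SAP*

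**What the plan says.** Section 8.2.6 ties the washout to the half-life of the analyte and then states: "At least 5 times elimination half-life is necessary. The wash out period for this study is three weeks". No value, source or analyte is given, although the product has two analytes. The synopsis (Study Procedures) adds only this: "After a washout period of three weeks, the study will be repeated in the same manner with the alternate drug". Neither place says whether the three weeks run from dose to dose or from the last sample, which section 8.1.5 puts at 72 h.

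Section 5.2 holds these half-lives:

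- Cyproterone acetate, Elimination text: serum levels fall in two phases with "half-lives of about 0.8 h and about 2.3 to 3.3 days".
- Cyproterone acetate, Table II (n=30 analysed): 116.81 ± 38.68 h for Diane 35 and 103.56 ± 24.84 h for that study's test product. The study enrolled "35 female postmenopausal healthy volunteers (aged 35-65 years") and its reference came from Schering France.
- Cyproterone acetate, Table IV (in-house pilot, n=6): 7.41 h test, 6.25 h Diane-35.
- Ethinylestradiol, Elimination text: about 24 h.

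Section 8.5 keeps a subject's data unadjusted if "the pre-dose concentration is equal to or less than 5% of the" Cmax for that period, and drops the subject above that limit. Section 8.6.1 gives an LLOQ of 0.4 ng/ml for cyproterone acetate.

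**The concern.** In a two-period crossover the washout is what protects the treatment comparison from carry-over. The plan calls five half-lives necessary, yet one of its own background tables, with the larger of the two datasets on the reference product, gives a half-life for which three weeks is too short. The three sources run from about 6 h to about 117 h, so the choice of source decides whether the rule is met, and 8.2.6 does not state the choice. If drug from period 1 were still present in period 2, the AUC values could be inflated, and unequal inflation for the two products would bias the ratio.

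**Working it through.** **Step 1. The rule against each source.** Required washout = 5 × t½, compared with 3 × 7 × 24 = 504 h dose to dose, or 504 + 72 = 576 h between doses if counted from the last sample.

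| Source | t½ (h) | 5 × t½ | 504/t½ | 576/t½ |
|---|---|---|---|---|
| Ethinylestradiol, text | 24 | 120 h (5.0 d) | 21.0 | 24.0 |
| Cyproterone, text, low | 55.2 | 276 h (11.5 d) | 9.13 | 10.4 |
| Cyproterone, text, high | 79.2 | 396 h (16.5 d) | 6.36 | 7.27 |
| Cyproterone, pilot reference | 6.25 | 31.3 h (1.3 d) | 80.6 | 92.2 |
| Cyproterone, pilot test | 7.41 | 37.1 h (1.5 d) | 68.0 | 77.7 |
| Cyproterone, Table II test | 103.56 | 517.8 h (21.6 d) | 4.87 | 5.56 |
| Cyproterone, Table II Diane 35 | 116.81 | 584.1 h (24.3 d) | 4.31 | 4.93 |

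The plan shows no derivation of three weeks, so there is no figure to reproduce. The interval is consistent with the Elimination text, with 21 − 16.5 = 4.5 days to spare.

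**Step 2. How firm the Table II shortfall is.** The longest half-life that fits the rule is 504/5 = 100.8 h or 576/5 = 115.2 h. Standard errors of the Table II means are 38.68/√30 = 7.1 h and 24.84/√30 = 4.5 h.

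- Diane 35, dose to dose: 116.81 − 100.8 = 16.0 h, about 2.3 SE. A clear shortfall.
- Diane 35, from the 72 h sample: 116.81 − 115.2 = 1.6 h, about 0.2 SE.
- Test product, dose to dose: 103.56 − 100.8 = 2.8 h, about 0.6 SE.

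Only the first can be told apart from meeting the rule.

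**Step 3. What would be left if Table II governed.** The last level follows from Ct = (AUCinf − AUCt) × ln 2 / t½, in ng and ml:

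- Diane 35: (428.49 − 327.89) × 0.693/116.81 = 0.597 ng/ml.
- Test: (403.15 − 318.21) × 0.693/103.56 = 0.569 ng/ml.

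The protocol does not give the last sampling time in Table II; I assume 72 to 192 h. The Diane 35 level at 504 h is then 0.597 × 2^(−432/116.81) = 0.046 to 0.597 × 2^(−312/116.81) = 0.094 ng/ml. At 576 h it is 0.030 to 0.061 ng/ml. The highest value is less than a quarter of the LLOQ (0.4/0.094 = 4.3) and 0.3% of the Table II Cmax (29.94 ng/ml).

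**Step 4. Effect on the AUC ratio.** The residual area over the next 72 h, as a share of Table II AUC0-t, is 0.82–1.68% after Diane 35 and 0.57–1.26% after the test product at 504 h. Each sequence carries one product's residue into the other's period, so the shift in the ln ratio is ½[ln(1 + cR) − ln(1 + cT)], which is 0.0013 to 0.0020 at 504 h and 0.0009 to 0.0015 at 576 h: about 0.1–0.2%.

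Table II AUC0-t is a generous denominator if sampling ran past 72 h. In the 192 h case, removing the 72–192 h area leaves 327.9 − 104.5 = 223.4 (Diane 35) and 318.2 − 104.7 = 213.5 h·ng/ml (test). The shares become 5.49/223.4 = 2.46% and 4.02/213.5 = 1.89%, and the shift ½[ln 1.0246 − ln 1.0189] = 0.0028, about 0.3%.

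**The case for a change.** The best case for acting is that the rule is worded as a requirement, the plan presents Table II without qualification as background on Diane 35, and the Diane 35 mean misses the rule on both ways of counting. A different population and manufacturer may be good reasons to set Table II aside, but the protocol never says so. Passing on the pilot reassures little, since its half-lives are roughly a tenth of those in the Elimination text. Individuals also vary: at the Diane 35 mean plus 1 SD (155.49 h), three weeks is only 504/155.49 = 3.24 half-lives. And the 5% pre-dose limit cannot show that the rule was met, because the projected residue is too small to quantify.

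Much of this stands. The input is not documented, the sources are not reconciled, and the start of the interval is not defined. What does not follow is that the plan breaks its rule. Nothing in 8.2.6 points to Table II or requires the longest cited value, and the text headed Elimination supports three weeks. The upper value there (79.2 h) lies within 1 SD of both Table II means (116.81 − 38.68 = 78.1 h; 103.56 − 24.84 = 78.7 h), so the sources are not far apart given their spread. For the slow eliminator, the same Table II last level taken at 192 h gives 0.597 × 2^(−312/155.49) = 0.149 ng/ml, still below the LLOQ. That the residue cannot be quantified is itself a sign of how small it is; a materially larger one would be caught by the 5% rule.

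**Conclusion.** No change to the plan follows. The arithmetic behind the concern is right, but it exposes a missing cross-reference, not an error. Three weeks meets the five-half-life rule for ethinylestradiol and on two of the three cyproterone acetate sources. It misses clearly only on the Table II Diane 35 mean counted dose to dose (4.31 half-lives). Naming the half-life and the counting convention would tidy 8.2.6, but it would alter no analysis and no conclusion. A reader can find in section 5.2 a half-life that supports the interval.

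On the least favourable source, the residue stays at or below 0.094 ng/ml and the AUC ratio moves by about 0.1–0.2% (0.3% on the stricter denominator), against acceptance limits of 80.00–125.00%. The size rests on three assumptions: a last Table II sample between 72 and 192 h, log-linear decline after it, and Table II means standing for the typical subject. None of this says which half-life is correct or that another interval is needed.
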